#### **Risk of confidentiality:**

Loss of confidentiality is another risk associated with this study, although this risk will be minimized by the use of a unique study number and password protected and encrypted databases. Data extracted for analysis will also be de-identified and personal identifiers will only be available to study staff.

#### **EXPECTED BENEFITS**

Participants have the potential to experience reduced pain symptoms during and after the VR experience. This result is very probable. Previous experiences suggest that the magnitude of this effect is, on average, large, and that the duration will be during the Virtual Reality experience and possibly up to a few hours or days afterwards.

#### **EQUITABLE SELECTION OF SUBJECTS**

The subjects recruited based on whether or not they meet the inclusion criteria above. These patients include people of all socioeconomic and ethnic categories, and no exclusions are made based on race, sex, or socioeconomic status.

#### **RECRUITMENT PROCEDURES**

We will recruit directly from the Pain Management Center through posted advertisements and ads on the waiting room TV. We will use the MGB Rally advertising platform to

provide interested subjects with information about the study, subjects can then provide their contact information.

Subjects will receive up to a total of \$40 for participating in this study. Subjects will receive \$30 for completing the Study Visit, and \$10 for completing the final survey after the Visit. The payment will be in the form of an Amazon Gift card given at the end of the study. If subjects withdraw before completing the study visit, they will not receive payment.

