### SPECIFIC AIMS

1. The purpose of this project is to evaluate the feasibility and effectiveness of VR as a treatment option for older adults with chronic osteoarthritic knee pain.
2. Aim 1: Implement a pilot study and collect data on the feasibility of VR and its effects on pain for older adults with chronic osteoarthritic knee pain.
3. Aim 2: Analyze the feasibility of VR for this population, including looking at simulation sickness factors and drop out reasons/rates, and its impact on chronic pain immediately prior to and immediately post intervention, as well as a few days post intervention.
4. Sub-study Aim 1: The aim of this sub-study is to compare the effectiveness of a virtual reality meditation session and a non-immersive meditation session for improving pain, affect, and physiological vital stats in adults with fibromyalgia.
5. Sub-study Aim 2: We hypothesize that the VR meditation session will facilitate greater improvements in pain, affect, and physiological vital stats as compared to the non-immersive meditation intervention.

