## RESEARCH DESIGN AND METHODS

We will recruit 25 older adults with knee osteoarthritis from Brigham and Women's Hospital (BWH) to obtain 20 subjects with complete data collection. The sub-study will enroll 25 adults with fibromyalgia from BWH.

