### **Sub-study:**

#### Inclusion Criteria:

1. Adults ages 18 and older (no upper limit)
2. Diagnosis of fibromyalgia with a minimum baseline pain level of 3 on an NPRS
3. English-speaking
4. Willing and able to visit the Brigham and Women's Pain Management Center site on two separate occasions to participate in the sub-study

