## FORESEEABLE RISKS AND DISCOMFORTS

### Risks from VR:

Contact with objects: Participants' vision is occluded by the Virtual Reality (VR) headset. In general, they will perform the VR sitting, but the program may prompt them to move their arms and/or legs during the session.

Simulator Sickness: Some participants experience simulator sickness while in the VR experience particularly after prolonged exposure. Simulator sickness symptoms can include fatigue, headache, eye strain, difficulty focusing, increased saliva in mouth, sweating, or nausea. This risk is moderate. We have 3 methods to reduce this risk. 1) Dosage of VR for this study is between 10-20 minutes which has been reported as typically used in the literature, so risk for motion sickness is reduced. 2) Participants will complete the Simulator Sickness Questionnaire after each experience to monitor for motion sickness. 3) Participants can halt any VR at any time for any reason.

Seizures: Some people may experience severe dizziness, seizures, eye or muscle twitching or blackouts triggered by light flashes or patterns during the VR. This risk is quite small. We have 2 ways to reduce this risk: 1) People with a known risk for seizures

will be excluded from this study. 2) If a subject experiences any of these symptoms we will immediately stop the VR. We will provide any indicated immediate supportive care, we will recommend that they see a doctor, and they will be discontinued from the study.

VR headset may be uncomfortable: Some people may find wearing the headset uncomfortable. This risk is small. We have 2 methods to reduce this risk: 1) we will work with the participant to adjust the headset to be as comfortable as possible. 2) participants can stop the VR experience at any time for any reason.

Contamination: The VR headset is tightfitting and in close contact with the skin of the face. It is possible that participants may cross contaminate contagious skin or eye disorders. This risk is small. We have 2 methods to reduce this risk: 1) We will exclude people who have active, contagious skin or eye infections. 2) We will use a washable face protector for each visit. Each device will be wiped with antibacterial cleaners after each use.

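### The all-or-nothing visit payment gives subjects a reason not to leave during the visit, which may lower the within-visit drop-out that Aim 2 measures and sits in tension with the freedom to halt VR

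*Protocol*

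**What the plan says.** **Payment (Protocol, Recruitment Procedures).** The total is up to $40: "Subjects will receive \$30 for completing the Study Visit, and \$10 for completing the final survey after the Visit". Nothing is prorated: "If subjects withdraw before completing the study visit, they will not receive payment". The money comes late: "The payment will be in the form of an Amazon Gift card given at the end of the study".

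**Outcome (Specific Aims, Aim 2).** The feasibility analysis is described as "including looking at simulation sickness factors and drop out reasons/rates".

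**Safeguard (Foreseeable Risks and Discomforts, Risks from VR).** Simulator sickness is rated a moderate risk. One of three listed protections is "Participants can halt any VR at any time for any reason". Under the seizure heading, staff stop the VR if a subject has severe dizziness, twitching, blackout or similar symptoms, and that subject is also taken out of the study.

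**Sample (Research Design and Methods).** The knee osteoarthritis study recruits 25 "to obtain 20 subjects with complete data collection".

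**Sub-study (Inclusion Criteria).** Subjects must be able to attend "on two separate occasions to participate in the sub-study". The sub-study design sections describe no follow-up survey.

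**The concern.** The knee study has one in-person visit containing one VR session. Any drop-out caused by the VR experience during that session falls in the window that the forfeiture covers. A subject who feels unwell and would rather go home has a financial reason to stay, and no term of the payment rule pushes the other way. The rule therefore bears on a quantity that the study sets out to estimate.

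It also sits awkwardly beside the safeguard. The risk section tells subjects that they may stop VR whenever they like. The payment section makes the visit payment depend on completion and does not say whether stopping VR counts against it. A subject discontinued for seizure-type symptoms cannot complete the visit and, on the words of the payment section, has not earned the $30. Reporting such symptoms could thus cost the subject money.

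At stake are how the within-visit drop-out figure can be interpreted, and whether a stated protection is as free to use as it appears.

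**Working it through.** **1. The plan's own figure.** Inputs: 25 recruited and 20 complete (Research Design and Methods).
- Implied attrition = 1 - 20/25 = 20%, or 5 subjects.
- Check: 20/(1 - 0.20) = 25. This reproduces the target, but only as a consistency check, because the 20% is back-calculated and the protocol states no drop-out rate.

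**2. Share of pay at stake.** Inputs: $30 and $10 (Recruitment Procedures). 30/(30 + 10) = 75% depends on completing the visit.

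**3. What the payment rule does in each case.**

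| Subject | Visit payment on the protocol's wording |
|---|---|
| Completes VR and questionnaires | Paid |
| Halts VR, stays, completes the post-session questionnaires and interview | Not stated; the words allow payment |
| Halts VR and goes home | Visit not completed, unpaid |
| Discontinued for seizure-type symptoms | Visit not completed, $30 not earned; no exception given |
| Completes the visit, lost at home follow-up | Visit payment kept; only the $10 is lost |

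After the VR session the visit still includes 10-20 minutes of questionnaires and a recorded interview (Post-Intervention Surveys), so the third row is a realistic case. The last row shows that the forfeiture does not act on follow-up losses.

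**4. Possible size, under assumptions.** The documents give no figure for the effect of payment. Suppose that true drop-out is 20%, that a share v of it would occur within the visit, and that a share s of those would-be leavers stays for the money. Then observed drop-out = 20% x (1 - s x v).

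| s | v = 1 | v = 0.5 | v = 0 |
|---|---|---|---|
| 10% | 18% | 19% | 20% |
| 25% | 15% | 17.5% | 20% |
| 50% | 10% | 15% | 20% |
| 75% | 5% | 12.5% | 20% |

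Neither s nor v can be taken from the protocol. The table shows only that the direction is fixed and that the size could be anything from nothing to substantial.

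**5. Precision.** The exact (Clopper-Pearson) 95% interval for 5/25 is 6.8% to 40.7%. Every value in the table except 5% lies inside it. The trial itself could not separate a payment effect from sampling error.

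**6. Cost of paying those who do not complete.** 5 x $30 = $150. This is an upper limit at the implied attrition: it takes all five losses as falling within a visit that was started. Losses at follow-up would already have been paid.

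**The case against.** **Halting VR is not the same as withdrawing.** The risk section uses different terms for stopping the VR and leaving the study, and for seizure-type symptoms it treats them as two steps. Nothing says that a halt forfeits payment. This stands: a subject who halts and finishes the questionnaires may well be paid. A reader might infer that the protocol penalises every halt, and the text does not support that. What remains is that the effect of a halt is not stated, and that a subject who leaves early or is discontinued does not earn the payment.

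**No bias is shown.** A reader might infer that the drop-out rate is biased towards feasibility. The documents neither show nor size an effect of $30 on staying through a 10-20 minute session. This also stands: the supportable statement is that the rule may lower within-visit drop-out.

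**The allowance of five is not all within the visit.** Complete data also require the home surveys a few days later (Follow-Up Questionnaires), so it would be wrong to treat all five allowed losses as early leavers. This stands and limits how far the rule can reach.

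**Tolerability is measured in other ways.** Simulator sickness scores, open-ended feedback, willingness to use VR again and reasons for drop-out are all collected, so feasibility does not rest on the drop-out rate alone. This largely stands. The limit is that the sickness form comes after the session, so a subject who leaves mid-visit may have no score.

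**Counting rules may sit in a SAP.** How halts enter the analysis can properly be left there. The payment sentence, however, is fixed in the protocol.

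**Conclusion.** The point holds as a cheap improvement that should be made, not as a demonstrated bias. The payment rule creates a one-way incentive against leaving during the visit, covering $30 of $40. Any effect on within-visit drop-out would be downward. Its size is unknown, and drop-out after a completed visit is untouched by the forfeiture. The tension with the halting safeguard arises because the protocol does not say what a halt does to payment, and because early departure or discontinuation for symptoms leaves the visit payment unearned.

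This rests on reading payment for completing the visit literally, since the protocol gives no exception. If staff in practice pay subjects who stop early, the concern reduces to wording.

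Separately, and as a minor matter, one visit payment plus a final-survey payment does not fit a sub-study with two visits and no described follow-up survey. That gap says nothing about drop-out in the knee study.

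**What to change.** Replace the forfeiture sentence in Recruitment Procedures. Suggested wording: *The visit payment is made to every subject who attends and starts the visit. Halting VR, leaving early or being discontinued does not affect it.* Repeat the second sentence beside the halting safeguard in the risk section so that the two sections agree. The halting and discontinuation rules themselves stay as they are.

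Record VR halts and early departures separately, each with its reason, as feasibility events, so that stopping the VR is not merged with leaving the study or with loss at follow-up.

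Restate the sub-study payment per visit attended, and either remove the final-survey payment there or describe the survey it refers to.

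**Cost:** a small amendment to the payment text and a few payments for incomplete visits, at most $150 in the knee study at the implied attrition. The sub-study cost cannot be given, because no per-visit amount is stated. If the rule has to stay, the minimum is to state that halting VR is not withdrawal and to report the rate as drop-out under payment conditional on completion.

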## **CONSENT PROCEDURES**

Informed consent will be obtained by either a study physician or a research assistant associated with the study. A physician will be available at all times to answer questions that a subject may have. The subjects are given ample time to consider their participation and if they are hesitant, are encouraged to take the consent form home and read it carefully before making their final decision. No subjects are enrolled who are unable to provide consent.

## **DATA AND SAFETY MONITORING**

The principal investigator and the co-investigators will review data and safety monitoring on a weekly basis. The study will be terminated when the target enrollment is reached.

## **MONITORING AND QUALITY ASSURANCES**

Study outcomes will be collected via REDCap database. The trained staff who carry out the procedures will also carefully monitor the study throughout its duration. The team will evaluate the progress of the study, verify that the rights and well-being of the subjects are protected, verify that the reported clinical study data are accurate, complete and verifiable from source documents, and the conduct of the study is in compliance with the approved protocol and amendments.

## **PRIVACY AND CONFIDENTIALITY**

The identity of patients is not revealed to any outside sources. All patient identifiers will be kept in a separate secure file location, password protected on the MGB servers. Only certified and trained study staff will have access to the information.

During the 14-week study period, all study records will be stored in a locked file drawer accessible only to study personnel in the Brigham and Women's Pain Management Center Research Lab. Electronic records will be collected using REDCap and stored in a password protected files. No electronic addresses will be attached to material. After the 14-week study period all de-identified data will be shared with Tufts University, data will be retained

at Tufts in [name] or other secure storage used by the department for a period of 7 years.
